# **Evaluation of the Effect of Three Types of Rapid Maxillary Expanders (Conventional, Hybrid and MSE)**

**NCT05446714**

**Date of the document:14/5/2024**

### **Statistical analysis**

Data management and statistical analysis were performed using the Statistical Package for Social Sciences (SPSS) version 20. Data were explored for normality by checking the data distribution and using Kolmogorov-Smirnov and Shapiro-Wilk tests. Comparisons of normally distributed numeric variables between groups was performed by ANOVA test followed by Bonferroni post hoc test whenever a significance difference was detected. Pre and post values was compared by paired t test.

The mean difference was calculated by the formula:(Value after-value before)

Difference data were non-parametric and were compared between groups using Kruskal Wallis test.

All p-values are two-sided. P-values  $\leq 0.05$  were considered significant.

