## II- Outcomes

### I- Comparison between Hybrid and conventional hyrax groups

- **Molar distance:** There was no significant difference between groups in pre values ( $p= 0.094$ ). Regarding post treatment, The mean value recorded in Hybrid hyrax ( $52.21\pm2.59$ ) was significantly higher than that recorded in Butterfly hyrax ( $49.43\pm2.41$ ) ( $p= .016$ ). Moreover, there was a statistically significant difference between groups regarding the amount of change (difference) by treatment ( $p=0.000$ ), with the highest value recorded in MSE ( $8.88\pm1.58$ ), followed by Hybrid hyrax ( $7.24\pm1.77$ ) and the lowest value recorded in Butterfly hyrax ( $5.88 \pm 1.39$ ), (Table1, Fig.1, 11).
- **Premolar distance:** There was no significant difference between groups in pre values ( $p= 0.058$ ). Regarding post treatment, The mean value recorded in Butterfly hyrax ( $43.67\pm2.55$ ) and Hybrid hyrax ( $42.73\pm2.7$ ) was significantly higher than that recorded in MSE ( $38.46 \pm2.61$ ), ( $p= .000$ ). Moreover, the mean value of amount of change (difference) recorded in Butterfly hyrax ( $6.68\pm1.83$ ) and Hybrid hyrax ( $6.08\pm1.84$ ) was significantly higher than that recorded in MSE ( $4.43 \pm1.82$ ), ( $p= .005$ ). (Table1, Fig.1, 11).
- **Molar rotation:** There was no significant difference between groups, regarding pre and post values ( $p= 0.175$ ;  $p=0.207$  respectively in right side and  $p=0.06$ ;  $p=0.07$  in left side). There was no significant difference between groups regarding the amount of change (difference) by treatment ( $p=0.503$  in right side and  $p=0.757$  in left side), (Table 1, Fig 2,12)
- **Premolar rotation:** there was no significant difference between groups, regarding pre and post values for the right side ( $p= .566$ ;  $p=.609$  respectively) and the left side ( $p=.455$ ;  $p=.283$  respectively). Moreover, there was no statistically significant difference between groups regarding the amount of change (difference) by treatment in the right side and left sides ( $p=0.084$ ;  $p= .410$  respectively), (Table 1, Fig.3,12)

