- **Nasal floor molar:** There was no significant difference between groups in pre values ( $p= 0.058$ ) and post value ( $p=0.397$ ). There was a statistically significant difference between groups regarding the amount of change (difference) by treatment ( $p=0.000$ ), with the highest value recorded in MSE ( $4.38\pm0.85$ ), followed by Hybrid hyrax ( $2.6\pm1.04$ ) and the lowest value recorded in Butterfly hyrax ( $2.2\pm 1.49$ ), (Table 2, Fig.4, 13).
- **Nasal floor premolar:** There was no significant difference between groups in pre values ( $p= 0.701$ ). Regarding post treatment value, there was a statistically significant difference between groups ( $p=0.001$ ), with the highest value recorded in MSE ( $39.73\pm2.27$ ), followed by Hybrid hyrax ( $38.63\pm1.77$ ) and the lowest value

recorded in Butterfly hyrax ( $37.04 \pm 1.17$ ). Moreover, regarding the amount of change (difference) by there was a statistically significant difference between groups ( $p=0.000$ ), with the highest value recorded in MSE ( $4.87 \pm 0.62$ ), followed by Hybrid hyrax ( $3.43 \pm 0.74$ ) and the lowest value recorded in Butterfly hyrax ( $2.47 \pm 1.02$ ), (Table 2, Fig.4, 13).

- **Hard palate maxillary width 6:** There was no significant difference between groups in pre values ( $p= 0.083$ ). Regarding post treatment, the mean value recorded in MSE ( $64.31 \pm 1.8$ ) was not significantly different from butterfly Hyrax ( $63.59 \pm 2.15$ ), but was significantly higher than that recorded in Hybrid hyrax ( $62.04 \pm 2.68$ ), ( $p= .023$ ). The mean value of amount of change (difference) recorded in MSE ( $5.91 \pm 0.92$ ) was significantly higher than that recorded in Butterfly hydrax ( $3.37 \pm 0.96$ ) and Hybrid hyrax ( $3.17 \pm 1.54$ ), ( $p= .000$ ). (Table 2, Fig. 5, 14).
- **Hard palate maxillary width 4:** There was no significant difference between groups in pre values ( $p= 0.677$ ). Regarding post treatment, the mean value recorded in MSE ( $40.34 \pm 1.56$ ) was significantly higher than that recorded in butterfly hyrax ( $38.17 \pm 1.76$ ), ( $p= .002$ ). The mean value of amount of change (difference) recorded in MSE ( $6.35 \pm 1.25$ ) was significantly higher than that recorded in Butterfly hydrax ( $4.51 \pm 1.28$ ) and Hybrid hyrax ( $5.09 \pm 1.16$ ), ( $p= .001$ ). (Table 2, Fig. 5, 14).

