- **Molar inclination:** There was no significant difference between groups, regarding pre and post values ( $p= 0.353$ ;  $p=0.734$  respectively in right side and  $p=0.312$ ;  $p=0.892$  in left side). The mean value of amount of change (difference) recorded in MSE was significantly higher than that recorded in Butterfly hydrax and Hybrid hyrax, ( $p= .000$  in right side and  $p=0.003$  in left side). (Table 2, Fig 6, 15)
- **Premolar inclination:** There was no significant difference between groups, regarding pre values ( $p= 0.191$  in right side and  $p=0.355$  in left side). Post treatment, the mean value recorded in Butterfly hyrax was significantly higher than the other groups ( $p=0.003$  in right side and  $p=0.000$  in left side). The mean value of amount of change (difference) recorded in MSE was significantly higher than that recorded in Butterfly hydrax and Hybrid hyrax, ( $p= .000$  in right side and  $p=0.000$  in left side). (Table 2, Fig 7, 15)
- **Arch depth:** There was no significant difference between groups, regarding pre values ( $p= 0.064$ ). Post treatment, the mean value recorded in MSE was significantly lower than the other groups ( $p=0.007$ ). The mean value of amount of change (decrease) recorded in MSE was significantly greater than that recorded in Butterfly hydrax and Hybrid hyrax, ( $p= .000$ ), (Table 3, Fig 8, 16)

- **Incisor inclination:** There was no significant difference between groups, regarding pre and post values ( $p= 0.243$  and  $p=0.922$  respectively). The mean value of amount of change (decrease) recorded in MSE was significantly greater than that recorded in Butterfly hydrax and Hybrid hyrax, ( $p= .001$ ), (Table 3, Fig 9, 18)
- **Anterior suture opening:** There was no significant difference between groups, regarding pre values ( $p= 0.290$ ). The mean value recorded in MSE post treatment was significantly higher than that recorded in Butterfly hydrax and Hybrid hyrax, ( $p= .000$ ). The mean value of amount of change (increase) recorded in MSE was significantly higher than that recorded in Butterfly hydrax and Hybrid hyrax, ( $p= .001$ ), (Table 3, Fig 10, 18)

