- **Posterior suture opening:** All groups recorded a value ( $0\pm0.00$ ) pre-treatment. Post treatment, The mean value recorded in MSE was significantly higher than that recorded in Butterfly hydrax, while Hybrid hyrax recorded a significantly lower value than the other 2 groups ( $p= .000$ ). The mean value of amount of change (increase) recorded in MSE was significantly higher than that recorded in Butterfly hydrax; while Hybrid hyrax recorded a significantly lower value than the other 2 groups ( $p= .000$ ), (Table 3, Fig 10, 18)

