## II-Comparison between pre and post values Hybrid and conventional hydrax groups

Comparing the pre and post values revealed that the post treatment value was significantly higher in post value compared to the pre value in molar and premolar distance (Fig.1), right and left molar rotation (Fig.2), right and left premolar rotation (Fig.3), nasal floor first premolar and molar (Fig.4), hard palate maxillary width first molar and premolar (Fig.5), right and left molar inclination (Fig.6), right and left premolar inclination (Fig.7) and anterior and posterior suture opening (Fig.10). On the other hand, Arch depth and incisor inclination recorded significantly lower post value compared to the pre value (Fig. 8,9), (Table 1-3)

Table (1) Descriptive statistics and comparison between (ANOVA test) and within group (i.e. between pre and post value) (paired t test) regarding molar and premolar distance; molar and premolar rotation right and left

GROUP	Pre		Post		Amount of change (post-pre)			P Within group	
	Mean	Std. Dev	Mean	Std. Dev	Mean	Std. Dev	Median		
Molar distance	Butterfly hyrax	43.55	1.97	49.43 b	2.41	5.88 c	1.39	5.77	.000*
	Hybrid hyrax	44.79	4.27	52.21 a	2.59	7.42 b	1.77	7.50	.000*
	MSE	42.14	3.25	51.01 ab	2.56	8.88 a	1.58	8.95	.000*
	P value bet. groups	.094ns		.016*		.000*			
Premolar distance	Butterfly hyrax	36.99	4.60	43.67 a	2.55	6.68 a	1.83	6.20	.004*
	Hybrid hyrax	36.65	3.15	42.73 a	2.70	6.08 a	1.84	5.90	.002*
	MSE	34.03	3.12	38.46 b	2.61	4.43 b	1.82	4.85	.002*
	P value bet. groups	.058 ns		.000*		.005*			
Molar rotation right	Butterfly hyrax	58.32	4.68	59.57	4.74	1.25	.67	1.10	.000*
	Hybrid hyrax	61.50	4.54	62.54	4.42	1.04	.58	1.10	.000*
	MSE	61.95	7.38	62.99	7.26	1.04	.65	0.90	.000*
	P value bet. groups	.175ns		.207 ns		.503 ns			
Molar rotation left	Butterfly hyrax	59.75	5.31	61.17	5.27	1.42	.51	1.50	.000*
	Hybrid hyrax	64.31	5.57	65.55	5.46	1.25	.82	1.10	.000*
	MSE	60.43	5.65	61.90	5.54	1.48	1.06	1.20	.000*
	P value bet. groups	.060 ns		.070 ns		.757 ns			
Premolar rotation right	Butterfly hyrax	74.71	6.68	75.84	6.64	1.13	.40	1.10	.000*
	Hybrid hyrax	73.79	6.58	74.71	6.48	.93	.48	0.90	.000*
	MSE	76.43	7.60	77.21	7.60	.78	.42	0.75	.000*
	P value bet. groups	.566 ns		.609 ns		.084ns			
Premolar rotation left	Butterfly hyrax	74.23	6.40	75.27	6.33	1.05	.32	1.10	.000*

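### The SAP text says inclination change was significantly higher with MSE, but its own Table (2) shows MSE lowest on all four molar and premolar rows

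*SAP*

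**What the plan says.** In the SAP, under II- Outcomes, the molar inclination and premolar inclination bullets carry the same sentence: "The mean value of amount of change (difference) recorded in MSE was significantly higher than that recorded in Butterfly hydrax and Hybrid hyrax". The p-values attached are .000 (right) and .003 (left) for molars, and .000 on both sides for premolars. Both bullets refer to Table (2) of the outcomes part (the demographic part has its own Table (2)), and the p-values match that table's change column.

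The Statistical analysis section defines change: "The mean difference was calculated by the formula:(Value after-value before". It also names the test: "Difference data were non-parametric and were compared between groups using Kruskal Wallis test". It gives a Bonferroni post hoc test after ANOVA but names no pairwise procedure after Kruskal-Wallis.

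The pre/post section lists "right and left molar inclination (Fig.6), right and left premolar inclination (Fig.7" among the measurements that were higher after treatment. On post-treatment premolar values the narrative says: "Post treatment, the mean value recorded in Butterfly hyrax was significantly higher than the other groups".

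**The concern.** The narrative and the table it cites give opposite directions for the same four comparisons. The two bullets are the only prose statement of the between-group result for inclination change. A reader who relies on them learns that MSE tipped molars and premolars most, with p-values attached, whereas the tabulated data say it tipped them least. The protocol's aim is to compare the effects of these three expanders, so the direction of a between-arm difference is the substance of the report.

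**Working it through.** **Inputs.** Pre, post and change summaries are from the SAP outcomes Table (2). Group sizes of 15, 15 and 16 (Butterfly, Hybrid, MSE) are from the demographic tables.

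**1. Reproduce the printed changes (post mean minus pre mean).**

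| Row | Butterfly | Hybrid | MSE |
|---|---|---|---|
| Right molar | 24.24 − 18.58 = 5.66 | 23.27 − 18.43 = 4.84 | 22.82 − 20.74 = 2.08 |
| Left molar | 23.67 − 18.45 = 5.22 | 23.71 − 19.09 = 4.62 | 23.01 − 20.49 = 2.52 |
| Right premolar | 11.72 − 6.70 = 5.02 | 8.34 − 6.43 = 1.91 | 8.72 − 7.76 = 0.96 |
| Left premolar | 12.46 − 7.37 = 5.09 | 8.63 − 6.57 = 2.06 | 8.41 − 7.61 = 0.80 |

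All twelve agree with the printed changes within 0.01, and all are positive.

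**2. Direction, from the printed changes.**

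| Row | MSE − Butterfly | MSE − Hybrid | Medians (Butterfly/Hybrid/MSE) | Letters |
|---|---|---|---|---|
| Right molar | −3.58 | −2.77 | 5.80/6.00/1.70 | a/a/b |
| Left molar | −2.69 | −2.10 | 6.30/4.90/2.35 | a/a/b |
| Right premolar | −4.06 | −0.95 | 5.90/1.60/0.90 | a/b/b |
| Left premolar | −4.29 | −1.26 | 5.80/2.20/0.70 | a/b/c |

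All eight differences are negative. On the right premolar, MSE and Hybrid share a letter, so the table does not support a significant difference there in either direction.

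**3. Could the arm labels in the table be wrong instead?** Steps 1 and 2 would survive swapped labels. Two checks bear on this.

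- *Molars.* Only MSE has 16 patients, so the baseline ANOVA shows which row carries n = 16 (assuming all 46 patients were analysed). For right molar baseline the grand mean is (15×18.58 + 15×18.43 + 16×20.74)/46 = 19.28. The between-group mean square is 26.15 and the within-group mean square is (14×4.41² + 14×5.33² + 15×5.06²)/43 = 24.51. Then F = 1.07 and p = 0.353, as printed. The ranges below allow for rounding of the printed means and SDs.

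| Baseline row | Printed p | n = 16 on MSE | on Butterfly | on Hybrid |
|---|---|---|---|---|
| Right molar | .353 | 0.349–0.357 | 0.359–0.367 | 0.361–0.369 |
| Left molar | .312 | 0.308–0.317 | 0.316–0.325 | 0.318–0.328 |

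Only the row labelled MSE fits.

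- *Premolars.* The narrative itself puts Butterfly significantly highest after treatment, with no significant baseline difference. That fits the table and sits badly with MSE having the largest rise. The n = 16 check does not separate MSE from Hybrid here: printed .191 fits MSE (0.184–0.196) and Hybrid (0.187–0.200), and printed .355 fits MSE (0.351–0.369) and Hybrid (0.339–0.358).

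**4. Indicative pairwise tests.** Kruskal-Wallis needs patient data, so these are t tests on the summaries. Bonferroni p = 3 × two-sided p. The pooled version uses SE = √[MSW(1/16 + 1/15)] on 43 df. For right molar, MSW = 2.778 and SE = 0.599, so MSE vs Butterfly gives t = −3.58/0.599 = −5.98.

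| Row | MSE vs Butterfly (pooled; Welch) | MSE vs Hybrid (pooled; Welch) |
|---|---|---|
| Right molar | 1e-6; 4e-7 | 0.0001; 0.0006 |
| Left molar | 0.0014; 0.0077 | 0.015; 0.0015 |
| Right premolar | 1e-9; 1e-5 | 0.195; 0.009 |

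The right premolar MSE–Hybrid result depends on the test. The pooled SD of 1.40 is driven up by Butterfly's 2.18.

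**5. Left premolar SDs.** The change SDs repeat the means in all three arms (5.09, 2.06, .80). The implied pre/post correlation is (SDpre² + SDpost² − SDchange²)/(2·SDpre·SDpost), which gives −0.49, 0.12 and 0.93. The other nine inclination cells give 0.81 to 0.98. With the SDs as printed, MSE vs Butterfly is 0.0015 pooled and 0.017 Welch. If correlations of 0.81 to 0.98 are assumed, the pooled change SD runs from 1.52 down to 0.77. MSE vs Hybrid is then 0.079 down to 0.0001 pooled and at most 0.015 Welch; MSE vs Butterfly is at most 2e-9 pooled and 2e-6 Welch.

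**The case against.** The strongest reply is that this is a wording slip in a results narrative. It alters no hypothesis, test, sample size or overall p-value. The sentences cite a table whose means, medians and letters agree with one another, and the premolar bullet itself warns the reader by placing Butterfly highest after treatment. Tooth inclination is not among the protocol's listed secondary outcomes. All of this is true and limits the reach of the error. It does not make the sentences right, and since the protocol names no specific primary variable, inclination cannot be set aside as outside the effect under study.

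Three narrower objections stand:

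- On premolars, the ordering of MSE below Hybrid rests on the printed labels alone. The statement that MSE exceeded Butterfly is contradicted under either labelling.
- None of the three left premolar SDs should be accepted as printed, although the MSE value implies a plausible correlation. A mean of .80, SD of .80 and n = 16 give t = 4.0 and a paired p of 0.0012, against a printed .000. The within-group p-values are not a dependable guide either: Butterfly premolar distance (6.68, SD 1.83, n = 15) gives t of about 14 but prints .004.
- The posterior suture text is a conflict of the same kind. It says "while Hybrid hyrax recorded a significantly lower value than the other 2 groups", while Table (3) has Butterfly lowest (2.14, 3.06, 5.16; letters c, b, a). It concerns a different outcome and leaves MSE highest in both places, but it also needs settling against source data.

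**Conclusion.** The concern holds. The direction of the MSE comparison is reversed in the text on four of four inclination rows, by 2.69 to 4.29 against Butterfly and 0.95 to 2.77 against Hybrid. The definition of change and the positive sign of every change rule out a sign convention. The evidence points to the sentences rather than the table. For molars this rests on the n = 16 check, which assumes ANOVA on all 46 patients. For premolars it rests on the narrative's own post-treatment statement, which identifies Butterfly only. Source data must decide.

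The direction does not depend on the t tests or on the doubtful left premolar SDs. Significance of MSE against Hybrid on premolars does depend on the pairwise procedure, which the SAP does not name for change scores. The duplicated SDs do not by themselves show that the left premolar letters or p-value are wrong.

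**What to change.** 1. Check both inclination bullets and the outcomes Table (2), including arm labels, against the dataset.
2. If the table is confirmed, restate the results. Molar change was significantly lower in MSE than in Butterfly and Hybrid on both sides. Premolar change was lowest in MSE and significantly lower than in Butterfly on both sides.
3. Name the pairwise procedure used after Kruskal-Wallis, and report MSE against Hybrid for right and left premolars from it.
4. Check all three left premolar change SDs against the output and correct them. Confirm that row's letters and p-value from the existing output, and re-run only if that is not possible.
5. Reconcile the posterior suture order between the text and Table (3) against source data.

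Proofreading in the same pass: the Butterfly and Hybrid changes for hard palate width 6 are exchanged between text and table (3.37/3.17 against 3.17/3.37). Hybrid molar distance change is 7.24 in the text and 7.42 in Table (1). The incisor post-treatment p is .922 in the text and .992 in Table (3); the summaries give 0.991. The anterior suture change p is .001 in the text and .000 in Table (3).

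The cost is a check of existing data and output, a few corrected figures and some rewording. No new data collection is needed.

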	Hybrid hyrax	76.99	6.07	78.65	5.55	1.65	2.50	1.10	.000*
	MSE	75.14	5.83	76.16	5.95	1.02	.47	1.10	.000*
	P value bet. groups	.455ns		.283ns		.410ns			

Significance level p≤0.05, \*significant, ns=non-significant

Post hoc test: Within the same comparison, means sharing the same superscript letter are not significantly different

Table (2) Descriptive statistics and comparison between (ANOVA test) and within group (i.e. between pre and post value) (paired t test) regarding nasal floor, hard palate maxillary width molar and premolar; molar and premolar inclination right and left

GROUP	Pre		Post		Amount of change (post-pre)			P Within group	
	Mean	Std. Dev	Mean	Std. Dev	Mean	Std. Dev	Median		
Nasal floor 1 st .molar	Butterfly hyrax	65.13	5.07	67.33	1.67	2.20 b	1.49	1.80	.003*
	Hybrid hyrax	63.48	3.13	66.08	2.80	2.60 b	1.04	2.40	.000*
	MSE	62.00	3.36	66.38	3.07	4.38 a	.85	4.45	.000*
	P value bet. groups	.058ns		.397ns		.000*			
Nasal floor 1 st .premolar	Butterfly hyrax	34.57	1.55	37.04 c	1.17	2.47 c	1.02	2.40	.001*
	Hybrid hyrax	35.21	2.09	38.63 b	1.77	3.43 b	.74	3.50	.000*
	MSE	34.86	2.40	39.73 a	2.27	4.87 a	.62	5.00	.000*
		.701ns		.001*		.000*			
Hard palate Maxillary width 6	Butterfly hyrax	60.43	2.49	63.59 ab	2.15	3.17 b	1.54	3.10	.000*
	Hybrid hyrax	58.67	2.99	62.04 b	2.68	3.37 b	.96	3.40	.000*
	MSE	58.39	2.44	64.31 a	1.80	5.91 a	.92	6.10	.000*
	P value bet. groups	.083ns		.023*		.000*			
Hard palate Maxillary width 4	Butterfly hyrax	33.66	1.85	38.17 b	1.76	4.51 b	1.28	4.50	.001*
	Hybrid hyrax	34.22	1.79	39.31 ab	1.39	5.09 b	1.16	4.90	.001*
	MSE	33.99	1.58	40.34 a	1.56	6.35 a	1.25	6.10	.003*
	P value bet. groups	.677ns		.002*		.001*			
Right.1 st molar inclination	Butterfly hyrax	18.58	4.41	24.24	5.32	5.66 a	1.52	5.80	.000*
	Hybrid hyrax	18.43	5.33	23.27	5.20	4.85 a	2.10	6.00	.000*
	MSE	20.74	5.06	22.82	4.77	2.08 b	1.30	1.70	.000*
	P value bet. groups	.353ns		.734ns		.000*			
Left.1 st molar inclination	Butterfly hyrax	18.45	4.34	23.67	6.07	5.21 a	2.74	6.30	.000*
	Hybrid hyrax	19.09	3.08	23.71	3.68	4.62 a	1.62	4.90	.000*
	MSE	20.49	3.78	23.01	3.53	2.52 b	1.31	2.35	.000*
	P value bet. groups	.312ns		.892ns		.003*			

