Right.1 st premolar inclination	Butterfly hyrax	6.70	2.51	11.72 a	3.96	5.02 a	2.18	5.90	.000*
	Hybrid hyrax	6.43	1.56	8.34 b	1.63	1.91 b	.98	1.60	.000*
	MSE	7.76	2.16	8.72 b	2.37	.96 b	.51	0.90	.000*
	P value bet. groups	.191ns		.003*		.000*			
Left.1 st premolar inclination	Butterfly hyrax	7.37	2.39	12.46 a	3.48	5.09 a	5.09	5.80	.003*
	Hybrid hyrax	6.57	1.60	8.63 b	1.51	2.06 b	2.06	2.20	.000*
	MSE	7.61	2.17	8.41 b	2.08	.80 c	.80	0.70	.000*
	P value bet. groups	.355ns		.000*		.000*			

Significance level p≤0.05, \*significant, ns=non-significant

Post hoc test: Within the same comparison, means sharing the same superscript letter are not significantly different

Table (3) Descriptive statistics and comparison between (ANOVA test) and within group (i.e. between pre and post value) (paired t test) regarding arch depth; incisor inclination

GROUP	Pre		Post		Amount of change (post-pre)			P Within group	
	Mean	Std. Dev	Mean	Std. Dev	Mean	Std. Dev	Median		
Arch depth	Butterfly hyrax	26.92	2.87	26.19 a	2.47	-.74 a	.38	-.70	.000*
	Hybrid hyrax	25.93	2.47	25.39 a	2.43	-.53 a	.22	-0.50	.000*
	MSE	24.72	2.25	23.38 b	2.41	-	.60	-1.30	.000*
	P value bet. groups	.064ns		.007*		.000*			
Incisor inclination	Butterfly hyrax	117.31	3.65	114.46	3.37	-	2.00	-2.80	.000*
	Hybrid hyrax	118.45	4.29	114.67	4.30	-3.79 a	1.80	-3.70	.000*
	MSE	120.05	5.32	114.63	5.79	-	1.48	-5.30	.000*
		.243 ns		.992 ns		.001*			
Anterior suture opening	Butterfly hyrax	.09	.27	3.57 b	.47	3.47 b	.34	3.50	.004*
	Hybrid hyrax	.27	.44	3.93 b	.64	3.67 b	.36	3.70	.000*
	MSE	.30	.42	5.99 a	.46	5.69 a	.33	5.70	.002*
	P value bet. groups	.290 ns		.000*		.000*			
Posterior suture opening	Butterfly hyrax	.00	.00	2.14 c	.44	2.14 c	.44	2.20	.000*
	Hybrid hyrax	.00	.00	3.06 b	.37	3.06 b	.37	3.10	.000*
	MSE	.00	.00	5.16 a	.49	5.16 a	.49	5.05	.000*
	P value bet. groups	---		.000*		.000*			

Significance level p≤0.05, \*significant, ns=non-significant

Post hoc test: Within the same comparison, means sharing the same superscript letter are not significantly different

[figure not shown]

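### Post-treatment arch depth is reported as significantly lower in MSE than in Hybrid, but the SAP's own Bonferroni rule gives p = .080; the nasal floor premolar letters make a similar unsupported claim (p = .29)

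*SAP*

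**What the plan says.** The SAP's Statistical analysis section sets the rule for comparing groups: "ANOVA test followed by Bonferroni post hoc test whenever a significance difference was detected". It adds that "All p-values are two-sided", and the table footnotes give "Significance level p≤0.05". The footnotes also explain the letters: "Within the same comparison, means sharing the same superscript letter are not significantly different". Two arms with no letter in common are therefore being reported as significantly different.

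Two post-treatment rows matter here.

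- **Arch depth.** The text under II- Outcomes reads "Post treatment, the mean value recorded in MSE was significantly lower than the other groups ( $p=0.007". Table 3 letters Butterfly a, Hybrid a and MSE b.
- **Nasal floor, first premolar.** Table 2 letters Butterfly c, Hybrid b and MSE a, which claims that all three pairs differ. The text is more cautious and only ranks the arms: "Regarding post treatment value, there was a statistically significant difference between groups ( $p=0.001$ ), with the highest value recorded in MSE".

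**The concern.** The arch depth sentence makes two pairwise claims, MSE below Butterfly and MSE below Hybrid, and supports both with one p-value. Table 3 prints that value in its between-groups row, so it is the overall test. An overall p of 0.007 does not show which pairs differ, and the Hybrid–MSE gap is the smaller of the two.

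The trial exists to compare three expanders, so a wrong statement that two of them differ is a wrong head-to-head result. A reader cannot see the error from the page, because no pairwise p-value is printed.

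**Working it through.** **Inputs.** Means and SDs come from SAP Tables 2 and 3 (post-treatment columns). Group sizes of 15, 15 and 16 come from the cross bite and malocclusion tables. No n is given per outcome, so these sizes are an assumption. B = Butterfly, H = Hybrid, M = MSE.

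| Row (post) | B | H | M |
|---|---|---|---|
| Arch depth | 26.19 (2.47) | 25.39 (2.43) | 23.38 (2.41) |
| Nasal floor premolar | 37.04 (1.17) | 38.63 (1.77) | 39.73 (2.27) |
| Hard palate width 4 | 38.17 (1.76) | 39.31 (1.39) | 40.34 (1.56) |

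**Formulas.** Within-group mean square MSW = Σ(nᵢ−1)SDᵢ² / (N−3), with N−3 = 43. F = (between-group sum of squares / 2) / MSW. For each pair, t = difference / √[MSW(1/nᵢ + 1/nⱼ)], and the two-sided p is multiplied by 3.

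**Step 1: reproduce the printed overall p-values.**

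- Arch depth: MSW = (14×2.47² + 14×2.43² + 15×2.41²)/43 = 255.20/43 = 5.935. F = (65.41/2)/5.935 = 5.51, p = .0074. The SAP prints .007.
- Nasal floor premolar: MSW = 140.32/43 = 3.263. F = (56.43/2)/3.263 = 8.65, p = .0007. The SAP prints .001.

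Both agree, so the means, SDs and group sizes are consistent with the reported overall tests.

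**Step 2: the Hybrid–MSE pairs.** The Bonferroni critical t on 43 df is 2.491.

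- Arch depth: difference 25.39 − 23.38 = 2.01; SE = √[5.935(1/15 + 1/16)] = 0.876; t = 2.30; unadjusted p = .027; Bonferroni p = .080. The interval is 2.01 ± 2.491×0.876, or −0.17 to 4.19. A difference of 2.18 would be needed for significance.
- Nasal floor premolar: difference 39.73 − 38.63 = 1.10; SE = √[3.263(1/15 + 1/16)] = 0.649; t = 1.69; unadjusted p = .097; Bonferroni p = .29. The interval is −0.52 to 2.72. A difference of 1.62 would be needed.

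**Step 3: all pairs (Bonferroni p).**

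| Row (post) | B–H | B–M | H–M | Printed letters B/H/M |
|---|---|---|---|---|
| Arch depth | 1.00 | .0075 | .080 | a / a / b |
| Nasal floor premolar | .061 | .0005 | .29 | c / b / a |
| Hard palate width 4 | .16 | .001 | .23 | b / ab / a |

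The last two rows of Table 2 are inconsistent with each other. With the same group sizes and degrees of freedom, Hybrid–MSE has t = 1.82 for hard palate width 4 and the arms share a letter. It has t = 1.69 for nasal floor premolar and they do not.

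**Step 4: sensitivity of the Hybrid–MSE p-values.**

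| Variant | Arch depth | Nasal floor premolar |
|---|---|---|
| Bonferroni, n 15/15/15 | .087 | .30 |
| Bonferroni, n 16/16/16 | .073 | .27 |
| Rounding of means and SDs | .077–.083 | .28–.30 |
| Tukey | .067 | .22 |
| Welch × 3 | .085 | .43 |
| Unadjusted | .027 | .097 |

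Only an unadjusted test puts arch depth below .05. Nothing tried does so for the nasal floor.

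**Step 5: check of the method.** The same calculation reproduces the printed letters in the other eight lettered post-treatment rows: molar and premolar distance, hard palate widths 6 and 4, right and left premolar inclination, and anterior and posterior suture opening. It also reproduces all 11 change-score rows with legible letters and usable SDs, including tight ones (molar distance B–H .033 and H–M .042; premolar distance H–M .048).

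**Step 6: change scores for the two rows, Hybrid against MSE.** Nasal floor premolar: 3.43 against 4.87, p < .001. Arch depth: −0.53 against −1.34 (23.38 − 24.72, because the printed MSE value is not legible), t = 5.19, p < .001.

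**The case against.** The strongest case on the other side is about weight. Change from baseline is the better measure of treatment effect, and on both outcomes the MSE–Hybrid difference in change is clear. Pre-treatment arch depth already differed in the same direction (Hybrid 25.93, MSE 24.72), so the final-value contrast partly reflects baseline. The protocol does not name arch depth as an outcome. All of this stands. It limits the consequence but does not make the sentence true.

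A second objection is that the nasal floor claim rests on superscripts alone, read from a PDF, with no prose to confirm it. That is a fair caution, and those letters should be checked against the source table. However, composite letters such as ab survive elsewhere in the same table, and nothing suggests that this cell was misread.

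Third, the two faults may have different causes. The arch depth letters match unadjusted tests, while the nasal floor letters match no test tried and are identical to the change-score letters in the same row, so a copied column is possible. The cause cannot be settled from the documents. What the two rows share is an MSE–Hybrid difference marked significant that the stated test does not support.

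Finally, attaching the overall p to pairwise statements is the report's habit throughout. Where the pairwise claims hold, that is a matter of style. The criticism here is confined to the arch depth sentence, where one of the two claims fails.

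**Conclusion.** The concern holds. Under the SAP's own rule, post-treatment arch depth in MSE is significantly lower than in Butterfly (p = .0075) but not than in Hybrid (difference 2.01, p = .080). The Table 3 letters for that row are wrong; a / ab / b would fit. The Table 2 letters for post-treatment nasal floor premolar wrongly separate MSE from Hybrid (difference 1.10, p = .29).

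These figures assume 15, 15 and 16 patients per row and a pooled error term. The conclusion on both Hybrid–MSE pairs survives the other group sizes, the rounding limits and the other multiplicity-adjusted tests tried.

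Butterfly–Hybrid on nasal floor premolar is borderline (.061 with the pooled error, .023 with Welch × 3), so that letter cannot be settled from summary data.

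The overall tests, MSE against Butterfly, and the MSE–Hybrid change-score differences are unaffected. The correction should be made, but it alters no conclusion about change.

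**What to change.** 1. Rerun the stated Bonferroni post hoc test on the data for the two rows, confirm the n in each, and take the letters directly from the output.
2. Replace the arch depth sentence, once the rerun confirms the values, with wording such as: *Arch depth after treatment differed between groups (ANOVA p = 0.007); MSE was significantly lower than Butterfly (Bonferroni p = .0075), while the difference from Hybrid was not significant (Bonferroni p = .080).* Here the overall p belongs to the overall statement and each pairwise claim has its own p.
3. As a minor side point, name the test behind the change-score letters. The Statistical analysis section says "Difference data were non-parametric and were compared between groups using Kruskal Wallis test" and gives no pairwise follow-up, while the captions refer to ANOVA, for example "Table (3) Descriptive statistics and comparison between (ANOVA test) and within group". The two should agree. No change-score letter was found to be wrong.

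The cost is a rerun of an existing test for two rows, two sets of letters, one sentence, and one line naming the change-score test. No new data are needed.
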